PROTOCOL TITLE: Coordinated medical treatment of opioid use disorder and infectious disease

Coordinating opioid use treatment through medical management with infection treatment (Project COMMIT)

PRINCIPAL INVESTIGATOR: [name]

NCT04180020

Project COMMIT Study Schedule

| Study Activities | Screening Process | | Study Entry | | Study Participation With Assigned Treatment | | | | | |
|--|-------------------|-----------|----------------------------------|----------------|---|-----|----------------|------|-------|-------|
| | Pre-Screening | Screening | Baseline Randomization/Induction | | Wk 1 | D/C | Wk 4 | Wk 8 | Wk 12 | Wk 24 |
| Intervention (LAB)^d | | | X | | | | X | X | | |
| Blood Buprenorphine Collection^a | | | X ^b | X ^b | | | X ^c | | | |
| Visit Number | | Visit 0 | Visit 1 | | Vis2 | | Vis3 | Vis4 | Vis5 | Vis 6 |
| Eligibility | | | | | | | | | | |
| Contact Primary Team | X | | | | | | | | | |
| Chart Review | X | | | | | | | | | |
| Review Inclusion/Exclusion | X | | | | | | | | | |
| Informed Consent | | X | | | | | | | | |
| Screener | | X | | | | | | | | |
| Laboratory Tests/Diagnostic Procedures | | | | | | | | | | |
| Urine Pregnancy Test | | X | | | | | X | X | X | X |
| Rapid HCV (confirmatory VL if applicable) | | | X | | | | | | X | |
| Rapid HIV (confirmatory test if applicable) | | | X | | | | | | X | |
| Urine Toxicology | | | X | | | | X | X | X | X |
| BMP (SOC) | | | X | | | | | | X | |
| CBC (SOC) | | | X | | | | | | X | |
| INR (SOC) | | | X | | | | | | | |
| LFTs (SOC) | | | X | | | | | | X | |
| HBV Core Ab, Hep B surface Ab, Surface Ag and reflex HBV DNA viral load for positive | | | X | | | | | | | |
| HIV VL (HIV+) | | | X | | | | | | X | |
| CD4+ Count (HIV+) | | | X | | | | | | X | |
| HCV VL (HCV+) | | | X | | | | | | X | |
| Interviews/Questionnaires | | | | | | | | | | |
| Demographics Form | | | X | | | | | | | |
| MINI (SUD, DSM-V d/o) | | | X | | | | | | | |
| AUDIT | | | X | | | | | | | |
| ASRS (for ADHD) | | | X | | | | | | | |
| WHOQOL-Bref | | | X | | | | X | X | X | X |
| PHQ-9 | | | X | | | | X | X | X | X |

| | | | | | | | | | |
|--|--|--|---|---|---|---|---|---|-----|
| PCL5 (PTSD) | | | X | | | | | | X |
| Modified PEG Pain Scale | | | X | | | X | X | X | X |
| Sexual Risk and IDU Risk Behaviors | | | X | | | X | X | X | X |
| Criminal Justice Questionnaire | | | X | | | X | X | X | X |
| Interpersonal Violence | | | X | | | X | X | X | X |
| Timeline Followback | | | X | | | X | X | X | X |

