If any of the above study assessments reveal presence of an exclusion criteria that was not initially revealed on screening, the participant will be informed and removed from the study.

Follow-Up

The following measurables will occur on each of the specified research study visits.

Week 1:

- Study Assessments: none
- Clinical: COWS, Opioid Craving, Ramsay sedation scale

Week 4:

- Study Assessments: WHOQOL-Bref, PHQ-9, Modified PEG Pain scale, Sexual and IDU risk behaviors, criminal justice questionnaire, Interpersonal Violence questionnaire, TLFB, medical/ID questionnaire, AUDIT, covid-19 Questionnaire, SUTx Form, modified SAFTEE
- Clinical: COWS, Opioid Craving, Ramsay sedation scale
- Laboratory: Urine pregnancy test, urine toxicology. The following labs will be collected if ordered by the clinical non-research team: basic metabolic panel (BMP), complete blood count (CBC), liver function tests (LFTs), and coagulation studies (INR).

Week 8:

- Study Assessments: WHOQOL-Bref, PHQ-9, modified PEG Pain scale, Sexual and IDU risk behaviors, criminal justice questionnaire, Interpersonal Violence questionnaire, TLFB, medical/ID questionnaire, AUDIT, covid-19 Questionnaire, SUTx Form, modified SAFTEE
- Clinical: COWS, Opioid Craving, Ramsay sedation scale
- Laboratory: Urine pregnancy test, urine toxicology. The following labs will be collected if ordered by the clinical non-research team: basic metabolic panel (BMP), complete blood count (CBC), liver function tests (LFTs), and coagulation studies (INR).

Week 12:

- Study Assessments: WHOQOL-Bref, PHQ-9, PCL5, modified PEG Pain scale, Sexual and IDU risk behaviors, criminal justice questionnaire, Interpersonal Violence questionnaire, TLFB, medical/ID questionnaire, AUDIT, covid-19 Questionnaire, SUTx form, modified SAFTEE
- Clinical: COWS, Opioid Craving, Ramsay sedation scale
- Rapid or serum HCV AB with positive HCV viral load reflex confirmation, rapid or serum HIV p24AG/AB with positive HIV viral load reflex confirmation, CD4 and viral load for known patients with HIV, HBsAg, HBsAb, HBcAb, urine toxicology. The following labs will be collected if ordered by the clinical non-research team: basic metabolic panel (BMP), complete blood count (CBC), liver function tests (LFTs), and coagulation studies (INR).

Week 24:

- Study Assessments: WHOQOL-Bref, PHQ-9, modified PEG Pain scale, Sexual and IDU risk behaviors, criminal justice questionnaire, Interpersonal

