Secondary outcomes: 1) Days using opioids, and days injecting drugs per 28 days prior to each major assessment point (weeks 4, 8, 12, and 24 post randomization) (longitudinal, continuous); 2) Urine toxicology-confirmed abstinent (urine toxicology negative for illicit opioids, and self-report negative over past 7 (at week 1) or 30 days (weeks 4, 8, 12, 24) (longitudinal, binary); 3) Completion of the prescribed course of antimicrobial therapy (binary), Re-hospitalization for infection by week 12 (binary); 4) Days using other drugs/alcohol per 28 days prior to each assessment (longitudinal, continuous); 5) Urine toxicology positive for non-opioid drugs (longitudinal, binary); 6) Social functioning and quality of life (WHOQOL-Bref) at 12 and 24 weeks after randomization (longitudinal, continuous); 7) Modified PEG Pain Scale at each assessment (Longitudinal, continuous) 8) HIV risk behaviors—days in past 28 days of vaginal or anal sex without a condom at weeks 4, 8, 12, 24 (longitudinal, continuous); 8) Any needle sharing in past 28 days (longitudinal, binary); 9) Treatment satisfaction (via the TSR)¹² at 12 and 24 weeks (longitudinal, continuous); 10) Discharge “against medical advice” (binary); 11) Cure of index infection (binary); 12) HCV cure or link to treatment (binary); 13) HIV Viral suppression (Viral Load < 200 copies), if HIV positive (binary); 14) overall hospitalization by week 12; 15) ED visits by week 12; 16) Serious adverse events (SAFETEE and non-fatal and fatal overdose) (binary).

Additional variables: *Covariates, primary and secondary analyses: Stratification factors:* Site (3 sites: YNHH; Columbia/Penn State Hershey; South Carolina/Greenville) will be included as a fixed effect in all analyses. *Covariates:* In general, the baseline score for each outcome measure (where applicable) will be included as a covariate in outcome analyses. *Moderators:* A range of baseline moderator variables will be explored including 1) Demographic characteristics (gender, age, ethnicity, living situation (domiciled vs homeless); 2) Modified Pain PEG scores at baseline (continuous) 3) Evidence of fentanyl use at admission (urine toxicology, self-report) (binary); 4) Other substance use at baseline (any cannabis, any stimulant, any heavy drinking days; binary); 5) Probable major depression at baseline (binary based on PHQ score); 5) Type of infection (endocarditis/ osteomyelitis/bacteremia/ cellulitis/ etc.). *Mediators:* 1) Social functioning

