(WHOQOL-Bref); continuous); 2) Opioid craving (continuous); 3) Pain (Modified PEG scores; continuous).

Intent to Treat, Dropouts, and Missing Data: All analyses will be on the Intent-to-treat (ITT) sample, i.e., all randomized subjects (N=200) according to the treatment arm to which they were assigned. For the primary outcome and secondary outcomes related to treatment engagement, any patients lost to follow-up will be assumed not to be enrolled in treatment nor to have completed the antimicrobial course. Loss to follow-up will be minimized through collection of extensive locator information at baseline and proactive outreach, as described above. For the secondary outcomes related to substance use, missing data (patients who cannot be located) will be assumed to be opioid positive (not abstinent), a typical assumption which is reasonable based on the high rate of relapse among patients with OUD who discontinue medication treatment.^{14,44-46} For other secondary outcomes, missing data will be treated as missing at random. Longitudinal mixed effects models do not require complete data to provide estimates of the outcome, and the estimates are considered valid under the assumption that the data are missing at random.⁴⁷ We will additionally perform sensitivity analysis for the secondary outcomes to examine the influence on the outcomes of dropout and missing data by performing several imputation methods, for instance imputing missing weeks as all abstinent or all non-abstinent. Comparison of the inferences from assuming various models for the missingness provides a measure of the validity of the efficacy estimate from the initial model.

Significance Testing and Preliminary Analyses: All tests for main effects will be performed at two-sided significance level of 5%. Before performing specific analyses, we will examine the distributions of outcome measures and covariates and investigate for outliers. The distributions of continuous variables will be checked for normality, and transformed, if necessary. Distribution of demographic and other baseline variables will be examined and described in terms of means, standard deviations, proportions and 95% confidence intervals. Covariates will be examined for association with treatment outcome. Covariates associated with treatment outcome will be adjusted for in models used to test study hypotheses.

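### Quality of life is defined at weeks 12 and 24 only, so missing at random must hold without the week-4 and week-8 scores that the trial collects

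*Combined protocol and SAP*

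**What the plan says.** **Collection.** The Project COMMIT Study Schedule marks WHOQOL-Bref at baseline and weeks 4, 8, 12 and 24. The visit lists in section 10.0 (Follow-Up) agree. The week-4 list, for example, opens "Study Assessments: WHOQOL-Bref, PHQ-9, Modified PEG Pain scale, Sexual and IDU risk behaviors".

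**Outcome definition.** Section 12.0, Secondary outcomes, item 6: "Social functioning and quality of life (WHOQOL-Bref) at 12 and 24 weeks after randomization (longitudinal, continuous". Other items in the same list cover more visits. Opioid-use days are taken at "each major assessment point (weeks 4, 8, 12, and 24 post randomization) (longitudinal, continuous", and pain is "Modified PEG Pain Scale at each assessment (Longitudinal, continuous".

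**Missing data.** Section 12.0, Intent to Treat, Dropouts, and Missing Data: "For other secondary outcomes, missing data will be treated as missing at random". The stated support is that for longitudinal mixed models "the estimates are considered valid under the assumption that the data are missing at random". Imputation-based sensitivity analyses are promised for secondary outcomes. The one example given sets missing weeks to abstinent or to non-abstinent.

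**Model.** Section 12.0, Secondary outcomes: Statistical Models, lists treatment, site as a fixed effect and the baseline score as a covariate. Longitudinal outcomes use a GEE with AR(1) correlation together with a random intercept. No visit or treatment-by-visit term is listed.

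**The concern.** Missing at random is always conditional on what the model contains. If only weeks 12 and 24 are outcomes and baseline is a covariate, a patient seen at week 4 or 8 and never again has no outcome row. The assumption must then hold given arm, site, baseline and any added covariates. The scores closest to dropout, which are likely to predict it, are set aside.

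At stake is the quality-of-life part of Aim 3. Attendance could plausibly relate to quality of life differently by arm, because the schedule gives ID/LAB patients study injections at weeks 4 and 8 and TAU patients receive no study medication. That is a ground for caution, not evidence that it will happen. Section 12.0 gives no reason for leaving out the two earlier visits.

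**Working it through.** **1. The plan's own figures.** The documents give no SD, effect size, power or dropout rate for quality of life. The only power figure concerns the primary outcome: 100 per arm, 40% against 59.7%, two-sided 5%. With pooled variance and no continuity correction it reproduces (power 80.03%, odds ratio 2.22). It does not bear on this point.

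**2. Who contributes.** If a fraction d is permanently lost before week 12, 100(1 − d) patients per arm have an outcome row. With an assumed baseline correlation of 0.5, the difference detectable with 80% power is (1.960 + 0.842) × √(2/n) × √(1 − 0.5²) SD:

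| Lost | n per arm | Detectable difference (SD) |
|---|---|---|
| 0% | 100 | 0.343 |
| 10% | 90 | 0.362 |
| 20% | 80 | 0.384 |
| 30% | 70 | 0.410 |
| 40% | 60 | 0.443 |

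This is mostly the cost of the loss itself. Step 4 shows that the earlier visits recover little of it.

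**3. Bias.** All inputs are assumed except 100 per arm. The true week-12 effect is 0.4 SD, and loss occurs after week 4 or week 8. The log-odds of loss rise by 1 for each SD by which the last observed score is lower. There were 2,000 simulated trials per setting. The first figure in each cell is the bias (SD) of a week-12 analysis adjusted for baseline only. The second is the bias when weeks 4 and 8 are also used, by sequential regression for monotone missing data. The link is in TAU only.

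| Lost | Exchangeable 0.5 | Exchangeable 0.7 | AR(1) 0.7 |
|---|---|---|---|
| 10% | −0.024 / −0.001 | −0.022 / −0.002 | −0.037 / 0.000 |
| 20% | −0.049 / −0.003 | −0.039 / −0.001 | −0.076 / −0.003 |
| 30% | −0.071 / −0.002 | −0.061 / −0.003 | −0.108 / −0.002 |
| 40% | −0.099 / −0.006 | −0.076 / 0.001 | −0.149 / −0.003 |

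Monte Carlo error is at most about 0.17/√2000 = 0.004. With the same link in both arms, bias was 0.005 SD or less in size either way. A separate simulation (about 32% loss, link in TAU only, true effect 0.30 SD) gave −0.08 to −0.15 SD without weeks 4 and 8 and about zero with them. In that simulation bias was at most about 0.02 SD when the link was equal.

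**4. Precision.** Adding weeks 4 and 8 lowered the empirical standard error by about 0 to 5%. The largest gains were under AR(1), for example 0.160 to 0.152 at 30% loss unrelated to score.

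**5. Would adding visits to the planned model be enough?** AR(1) GEE was simulated with 600 trials per setting, about 30% loss, the link in TAU only, a true week-12 effect of 0.27 SD and an effect growing from week 4. With a single treatment term, weeks 4 to 24 gave estimates of 0.15 to 0.19 SD, against 0.13 to 0.18 for weeks 12 and 24. Under exchangeable correlation adding visits was slightly worse, because early visits dilute the estimate. With treatment-by-visit terms the estimates were 0.23 to 0.29. When the effect was constant over time, the single-term model did improve.

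**Limits.** Week 24 was not simulated in step 3, and lost patients were taken as never returning.

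**The case against.** - **Nothing bars weeks 4 and 8 from the model.** This is correct. The exclusion is read from an outcome definition that names visits, beside neighbours that name all of them. WHOQOL-Bref is also a listed mediator, so the early scores may have a use there. That use would not require leaving them out of the outcome model.
- **Choosing target visits is legitimate.** The aims are set at 3 months, and treatment satisfaction is also taken at weeks 12 and 24. This stands, but target visits can be kept as reported contrasts while the model uses every visit.
- **Loss may be small or temporary.** Field visits, telephone assessment and community tracking are planned. A reader might infer that anyone missing at week 12 adds nothing. The documents do not support that, because a patient seen at week 24 still has an outcome row.
- **Sensitivity analyses are already promised.** The commitment is broader than its abstinence example, so it is a partial safeguard. That example cannot be applied to a quality-of-life score, and no other method is named.
- **The harm needs a particular dropout pattern.** This stands in full and limits the verdict.

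**Conclusion.** The point holds as a conditional weakness in a secondary analysis. The plan collects scores that would make its missing-at-random assumption more credible and, on the natural reading, does not use them for this outcome.

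If dropout depends on quality of life differently by arm, the week-12 effect is biased by roughly 0.02 to 0.04 SD at 10% loss, 0.04 to 0.08 SD at 20%, and 0.06 to 0.15 SD at 30 to 40%. When low scorers leave TAU, the benefit of ID/LAB is understated; the reverse pattern would overstate it. If the link is equal in both arms, bias is near zero. These sizes rest on assumed loss rates, correlations and strength of link.

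A reader might infer two stronger things. One is that the planned estimate is biased by a set share of the effect. The documents give neither a dropout rate nor a mechanism, and any such share depends on the effect assumed: at 30% loss, 0.06 to 0.11 SD is 15 to 28% of an effect of 0.40 SD. The other is that naming two more visits in item 6 would cure the problem at no cost. Step 5 shows that it would not with a single treatment term. Moreover, unweighted GEE generally needs data missing completely at random.

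The primary analysis is unaffected.

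**What to change.** Change two paragraphs of section 12.0.

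1. **Secondary outcomes, item 6:** state that WHOQOL-Bref scores at weeks 4, 8, 12 and 24 all enter the model. The week-12 contrast is the Aim 3 estimate and week 24 is supportive.
2. **Secondary outcomes: Statistical Models:** for this outcome, replace the GEE AR(1) model with a single treatment term by one likelihood-based repeated-measures model with baseline score, site, visit and treatment-by-visit terms.

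The cost is a short text change in both places and slightly more modelling, with no new data. The change does not protect against dropout that depends on unobserved scores. A sensitivity analysis suited to a continuous score, such as delta-adjusted multiple imputation, would address that and could be named under the imputation methods already promised.

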12.0 Data Management

Power Analysis: Previous studies of buprenorphine initiation in an Emergency Department⁴² and on a medical inpatient service,⁴³ yielded rates of post-discharge buprenorphine maintenance treatment in the 70% range. The Emergency Department study implemented a Screening, Brief Intervention and Referral control condition, similar to the TAU condition planned in the current protocol, which yielded a rate of post-discharge buprenorphine maintenance treatment of 45%. We anticipate that the population recruited for this study will be among the most severely ill patients with OUD, being those requiring hospitalization for infections, and therefore we conservatively assume that the proportion of patients meeting our primary outcome (enrolled in MOUD 12 weeks after hospital discharge) will be 40% in the TAU arm and 60% in ID/LAB arm. We have chosen a sample size of N = 200 total (N = 100 per study arm), in order to ensure sufficient power (power = 80%) with a two-sided level of significance of 5% to detect a difference of at least 19.7% between the TAU and ID/LAB treatment groups (i.e., 40% treatment enrollment in the TAU arm and at least 59.7% treatment enrollment in the ID/LAB arm). This rate difference of 19.7% is equivalent to an odds-ratio of 2.2 and would be clinically meaningful.

Data Analysis Plan:

Primary outcome: The primary outcome will be a binary indicator of whether a patient is enrolled in and receiving effective MOUD (buprenorphine, methadone, or injection naltrexone) at 12 weeks (3 months) after randomization.

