Secondary outcomes: Statistical Models: For each of the secondary outcomes (see above) the effect of randomization to the ID/LAB arm compared to the TAU arm will be estimated with a model of the same general form as for the primary outcome (independent variables: treatment assignment (ID/LAB vs TAU), Site as a fixed effect, and baseline score as covariate where relevant) using logistic regression models (for binary outcomes), generalized linear model (for continuous outcomes), or longitudinal generalized mixed effects model (for longitudinal outcomes) with appropriate link functions (e.g. logit for binary outcomes). Longitudinal outcomes analyzed using a mixed effects models will utilize a generalized estimating equation with an autoregressive correlation structure (AR(1)) to account for within subject correlation over time, as well a random intercept accounting for between subject variability. In addition to site, covariates that are found to be related to the outcomes will be added to the models to improve the power for detecting significant differences.

Moderation and Mediation: Moderation Statistical Models: The effect of randomization to the ID/LAB vs TAU arms will be estimated for subpopulations based on the demographic and baseline characteristics selected as moderators (see above). We will estimate the moderation effect on primary outcome using a similar model to Aim 1 primary outcome with the inclusion of moderator by treatment interaction: $Y_i = \beta_0 + \beta_1 Trx_i + \beta_2 M_i + \beta_3 Trx_i M_i + \beta_4 C_i + s_i$ where M_i is the moderator status for i^{th} subject and Trx_i is subject's treatment assignment. Regardless of the significance of the interaction term, we will use the model to estimate the 95% confidence interval of the treatment effect for each level or category of the moderator variable, or the treatment effect at selected values of the moderator variable, if continuous. The moderator analyses are exploratory and hypothesis generating, but significant moderator effects can be useful in planning future efforts at implementation of medication treatment for opioid use disorder in medical settings by identifying subgroups that may particularly benefit. Identifying subgroups where there is less benefit may suggest future modifications to the implementation strategy to achieve better effect in those subgroups.

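### The depression moderator cuts the baseline PHQ-9 score to yes/no with no stated cut-off, although the full score is collected and the moderator model already accepts continuous moderators

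*Combined protocol and SAP*

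**What the plan says.** The study schedule and the baseline visit description in section 10.0 both include the PHQ-9, so every randomized patient should have a full baseline score.

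Section 12.0, under Additional variables, lists the moderators to be explored. Depression appears as "Probable major depression at baseline (binary based on PHQ score"). The score that separates yes from no is not stated there or elsewhere. In the same list the other symptom scale is left intact: "Modified Pain PEG scores at baseline (continuous").

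The moderation model in section 12.0 adds a moderator-by-treatment interaction to the primary model. It plans to report the effect for each category of a categorical moderator, "or the treatment effect at selected values of the moderator variable, if continuous". It also says "Regardless of the significance of the interaction term, we will use the model to estimate the 95% confidence interval" of the treatment effect across the moderator, and "The moderator analyses are exploratory and hypothesis generating".

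**The concern.** Splitting a graded score treats all patients on one side of the cut as alike. A patient just above the cut is grouped with the most severely depressed, and one just below it with those who have no symptoms. If the benefit of ID/LAB rises or falls steadily with depression severity, the split discards part of that signal, widens the interval for the interaction relative to its size, and makes a real gradient easier to miss. The trial was sized for a main effect in 200 patients, so there is little precision to spare for an interaction.

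The missing cut-off is a second weakness. A binary indicator described only as based on the PHQ score can be built in more than one way after the data are seen. The plan intends to use moderator results to identify groups that benefit more or less and to shape later implementation, so both precision and pre-specification have some value even in exploratory work.

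**Working it through.** **Inputs from section 12.0.** Sample size "N = 200 total (N = 100 per study arm"); 40% enrolled in medication treatment under TAU and 59.7% under ID/LAB; odds ratio 2.2; 80% power; two-sided 5%. That level is stated for the primary comparison and main effects; applying it to the interaction is an assumption. Patients lost to follow-up count as not enrolled, so all 200 stay in the model.

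**Not in the documents, so assumed and varied.** The PHQ-9 distribution, the cut-off, the share of patients above it, the interaction size, and the shape of the gradient.

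**Step 1: the plan's own figure.** With pooled variance, the mean rate is (0.40 + 0.597)/2 = 0.4985.

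- Standard error under no difference: √(2 × 0.4985 × 0.5015/100) = 0.0707
- Standard error under the alternative: √((0.40 × 0.60 + 0.597 × 0.403)/100) = 0.0693
- Power: Φ((0.197 − 1.96 × 0.0707)/0.0693) = Φ(0.84) = 0.80
- Odds ratio: (0.597/0.403)/(0.40/0.60) = 2.22

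The stated 80% and 2.2 reproduce. The plan gives no power for any interaction.

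**Step 2: information kept by the split.** For a normal score with a linear log-odds interaction, a cut with share p above it keeps φ(z_p)²/[p(1 − p)] of the information.

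- p = 0.5: 0.637, equivalent to 200 × 0.637 ≈ 127 patients
- p = 0.3: 0.576, equivalent to about 115 patients
- p = 0.2: 0.490, equivalent to about 98 patients

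Relative to the size of the effect, the interval is 1/√0.637 = 1.25 times as wide at 50/50 and 1/√0.576 = 1.32 times as wide at 30/70.

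**Step 3: power after the split.** With RE the share of information kept, power = Φ(√RE × (1.96 + z_power) − 1.96). For 80% continuous power at 50/50: Φ(0.798 × 2.802 − 1.96) = Φ(0.275) = 0.61.

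| Power with continuous score | 50/50 split | 30/70 split | 20/80 split |
|---|---|---|---|
| 80% | 61% (−19) | 57% (−23) | 50% (−30) |
| 50% | 35% (−15) | 32% (−18) | 28% (−22) |
| 30% | 21% (−9) | 19% (−11) | 17% (−13) |
| 20% | 14% (−6) | 13% (−7) | 12% (−8) |

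**Step 4: check by simulation.** Logistic model with site as a fixed effect, 100 per arm, TAU 40%, main-effect odds ratio 2.25, normal score, 1,500 runs per scenario. Power is shown as continuous → binary.

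| Interaction, log-odds per SD | 50/50 | 30% above cut | 20% above cut |
|---|---|---|---|
| 0.40 | 27% → 19% | 28% → 18% | 27% → 14% |
| 0.60 | 51% → 37% | 51% → 31% | 49% → 24% |
| 0.90 | 81% → 61% | 81% → 54% | 78% → 41% |

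The simulation agrees with the formula at weak interactions. At stronger ones it gives similar or somewhat larger losses, up to 37 points in this table (0.90 with a 20/80 split).

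**Step 5: the opposite case.** If the true effect is a step exactly at the cut-off, the binary coding has the higher power. For step interactions of 0.9, 1.3 and 1.8 on the log-odds scale, power with continuous versus binary coding is 24% versus 35%, 44% versus 60% and 70% versus 86% at 50/50. It is 18% versus 30%, 29% versus 48% and 48% versus 72% with 30% above the cut. Binary coding gains about 11 to 25 points.

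**The case against.** The strongest reply is that nothing confirmatory rests on this analysis. It is labelled exploratory, no power is claimed, and intervals are reported whatever the interaction test shows. That stands, and it sets the priority of the point. It does not remove it: where intervals rather than tests are the product, their width matters.

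Second, probable major depression is a recognizable clinical category. Section 10.0 describes the PHQ-9 as a screen for major depression, and the moderation plan aims to find subgroups. Pain has no comparable diagnostic category in the documents, so the contrast with the pain score is only weak evidence of inconsistency. This also stands. It is a reason to keep the category as a subgroup display, but not to make an undefined cut the only form of the moderator.

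Third, the moderator list is open-ended, so a continuous PHQ-9 analysis is not ruled out. True, but nothing commits the team to one.

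Fourth, a reader might infer that the cut costs this trial a definite amount of power, say 13 to 25 points. The documents do not support that. They give no interaction size, score distribution, prevalence or cut-off, and the result moves from about 6 points to more than 30 across plausible inputs. A reader might also infer that binary coding is always the weaker choice; Step 5 shows that this depends on the shape of the effect. The documents state neither a threshold hypothesis nor a gradient.

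**Conclusion.** The point holds as a low-priority improvement. The plan reduces a score that it collects in full to an indicator whose cut-off it does not define, while its own moderation model could use the score as it is. The loss is conditional. With a roughly normal score and a roughly linear log-odds gradient, about 64% of the information remains at a 50/50 split and 58% at 30/70, and 80% power would become about 61% or 57%. It is about 6 to 13 points if the continuous test has only 20% to 30% power, which is possible in a trial sized for a main effect, and 30 or more at a 20/80 split when the continuous test has about 80% power. The sign reverses if the effect is a true step at the cut-off.

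The missing cut-off does not depend on any of these assumptions. Neither issue amounts to an error in a confirmatory analysis.

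**What to change.** In section 12.0, Additional variables, make the baseline PHQ-9 total score (continuous) the primary form of the depression moderator. Fit the planned interaction with that score and report the treatment effect with its 95% confidence interval at PHQ-9 values named in advance (for example 5, 10, 15 and 20). Check linearity, for instance with a quadratic term for the score and its interaction with treatment.

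Keep probable major depression as a secondary subgroup display, with its PHQ-9 cut-off written into the plan before the data are examined.

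The cost is a line or two of text and one extra exploratory model, with no new data and no change to sample size or conduct. The downside is reliance on a linear log-odds gradient; the quadratic check and the retained binary display partly cover it.
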